5 STUDY POPULATION

It is anticipated that this study will enroll a total of approximately 220 subjects. This includes 140 children in the vaccination cohort [20 children between 6-12 months, 60 children with a birth date after 2009 (35 children <3 years of age and 25 children \geq 3 years of age), 30 children with a birth date between 2006 and 2009, and 30 children with a birth date between 2003 and 2006]. We also will enroll up to 80 children total who present with acute influenza infection (20 children into each of the 4 age cohorts). We anticipate having to screen up to 500 children presenting with signs of ILI during the height of seasonal influenza circulation in order to identify and recruit these 80 children with natural influenza infection, as only a small number of children with symptoms possibly consistent with influenza will actually have respiratory infections as a result of influenza virus infection. It is anticipated approximately two-thirds of the children in all cohorts (both A and B) will enroll in the optional year of longitudinal follow-up.

The goal of this study is to understand the development of influenza-specific immunity in a population of children in the Rochester, NY area. Children will be excluded from participation in the study if they meet exclusion criteria of the protocol such as having a documented immunodeficiency or are on immunosuppressive medications expected to have a more than a minimal impact on the development of an immune response to vaccination or infection. Other conditions that may possibly have more than a minimal effect a child's immune system, such as allergies or other hypersensitivity syndromes, mild asthma, or obesity, will be able to enroll in the study. The presence or absence of concomitant medications and medical conditions will be documented and the effect of potential confounding variables will be examined in data analysis.

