11.2 Sample Size Considerations

Because the degree of variability in many of the measurements in this study are unknown, estimating with precision the correlation of patient characteristics (age and prior vaccination history) with outcomes (CD4 T cell response magnitude and function, antibody quality and quantity and B cell response) is not possible. The study will evaluate these outcomes and, if trends towards a relationship are discovered, subsequent studies will evaluate these in more detail.

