11.4 Final Analysis Plan

Data will be analyzed at the end of the study, with results available for publication at that time.

A cohort of n=20 to 60 healthy children that receive a prime-boost vaccination with IIV and n=20 children infected with influenza acutely will be recruited for each age cohort. Their T cell and antibody responses will be measured at three time points: baseline, day 8, and day 24 post-vaccination. We will apply Shapiro-Wilk's test to check the normality. If the data passes the normality test, two sample *t*-tests will be used to detect significant mean difference between the children of different ages and flu exposures at each time point. Otherwise, Wilcoxon rank-sum test will be used. For follow up visits, subjects will be followed longitudinally for one to two years with yearly revaccination with IIV. CD4 T cell responses (flow cytometry) and B cell and antibody responses will be measured at three time points: prior to IIV re-vaccination, 8 and 24 days post re-vaccination. We will apply one-way ANOVA *F*-test (or Kruskal-Wallis test, if the

normality assumption is rejected) to detect significant group differences at each time point. Because multiple response variables are used in this analysis, the p -values will be adjusted by the Benjamini-Hochberg multiple testing procedure [38] to control the false discovery rate (FDR) at the level of 0.05.

General linear models of difference or fold change in T/B cell response at following time points from baseline will be used to explore how childhood exposures affect immune responses over time, while controlling potentially confounding variables including age, sex, presence of asthma or allergies, or other acute or chronic illnesses and medications that may impact the immune response. In addition to time-specific comparisons, the following linear mixed effect model will be used to analyze data collected from all time points

$$y_{kit} = \alpha_k + \beta_{1k}G(i) + \beta_{2k}X_{kit} + \gamma_{kt} + \dot{\mathbf{0}}_{kit}. \quad (0.1)$$

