Here y_{kit} represents the k th response variable measured from the i th subject at the t th time point; α_k is the overall mean value of y_{kit} ; $G(i)$ is a binary variable which equals 0 if the i th subject is vaccinated with IIV and 1 otherwise; β_{1k} is a linear coefficient that quantifies the magnitude of the group-effect; β_{2k} are linear coefficients for potentially confounding clinical variables listed above; γ_{kt} is a random effect term that quantifies the time effects; and $\dot{\mathbf{0}}_{kit}$ represents independent measurement errors. Likelihood ratio test will be used to test $H_0 : \beta_k = 0$ against $H_1 : \beta_k \neq 0$.

In case of high-dimensional data in different scales, standardization will be applied before model fitting and variable selection. Variable selection approaches using AIC or BIC criteria will be used to select the significant predictors. Penalized-based variable selection procedures such as LASSO [39] or SCAD [40,41] may be used to overcome the drawbacks of ad-hoc methods of stepwise, best subset selection, etc. post-hoc.

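### Model (0.1) pools every visit but has no within-child term, so its test of infection against vaccination treats repeated samples from one child as independent

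*Combined protocol and SAP*

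**What the plan says.** Section 11.4 introduces the model thus: "In addition to time-specific comparisons, the following linear mixed effect model will be used to analyze data collected from all time points". Model (0.1) writes the k-th response of child i at time t as a mean αₖ, plus β₁ₖG(i), plus β₂ₖX, plus γₖₜ, plus an error.

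- G(i) is 0 for a child vaccinated with IIV and 1 otherwise.
- X holds measured confounders such as age, sex, asthma or allergies, illnesses and medications.
- γₖₜ "is a random effect term that quantifies the time effects". It is indexed by response and time, not by child.
- The error term "represents independent measurement errors".
- A likelihood ratio test is applied to βₖ, although the model defines only β₁ₖ and β₂ₖ.

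The same section also plans tests "to detect significant group differences at each time point", and "General linear models of difference or fold change in T/B cell response at following time points from baseline". It does not say whether these change models are fitted visit by visit or with visits pooled. Section 11.2 gives no variance or correlation: "Because the degree of variability in many of the measurements in this study are unknown".

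**The concern.** A time effect shared by all children correlates different children at the same visit. It does not connect one child's visits to each other. Given G and X, model (0.1) therefore counts a child's 3, 6 or (with the optional season) 9 samples as that many independent observations. β₁ₖ compares children with children, so it is the coefficient most exposed: its standard error is computed as if there were more independent units than there are.

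The study's own rationale (section 2.2) is that early exposures leave a lasting mark on a child's immunity, so positive residual correlation between a child's samples is to be expected. Model (0.1) is the plan's all-visit, covariate-adjusted test of infection against vaccination. If its p-values are too small, a false discovery rate adjustment cannot repair them, because that adjustment needs valid p-values as input.

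**Working it through.** The plan states no power, SD or correlation for this model, so there is no figure of its own to reproduce. The structure is read from section 11.4. The size of the effect is worked out over assumed ranges.

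**Inputs from the documents.** Section 5: "This includes 140 children in the vaccination cohort" (20 + 60 + 30 + 30 = 140) and up to 80 infected children (4 × 20 = 80). Section 11.4: 3 samples per season, so m = 3 in season 1, 6 over the main study and 9 with the optional season. These are planned maxima: draws are taken if able, and infected children may bypass visit 1.

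**Assumed.** Residual within-child correlation ρ (after X) from 0.1 to 0.7; arm SDs; how far correlation carries from one season to the next; a two-sided 5% test.

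**Formula.** True size = 2 × (1 − Φ(1.96/√(D × H))). D is the ratio of true to modelled variance caused by correlation. H is the ratio caused by unequal arm SDs and is 1 when they are equal.

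**Equal SDs**

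| Setting | D | ρ = 0.1 | 0.3 | 0.5 | 0.7 |
|---|---|---|---|---|---|
| 3 samples | 1 + 2ρ | 7% | 12% | 17% | 21% |
| 6 samples, no carry-over between seasons | 1 + 2ρ | 7% | 12% | 17% | 21% |
| 6 samples, half carried over | 1 + 3.5ρ | 9% | 17% | 24% | 29% |
| 6 samples, all carried over | 1 + 5ρ | 11% | 22% | 29% | 36% |
| 6 samples, equal correlation, a random 70% obtained | 1 + 3.5ρ | 9% | 17% | 24% | 29% |
| 9 samples, all carried over | 1 + 8ρ | 14% | 29% | 38% | 45% |

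Example: m = 6, ρ = 0.3 gives D = 2.5; 1.96/√2.5 = 1.24; size 21.5%.

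**Simulation check.** This used the maximum likelihood ratio test with a random time effect, no child term, no covariates and no true group effect (4,000 replicates, 140 v 80). At ρ = 0 / 0.1 / 0.3 / 0.5 / 0.7 the size was 5.2 / 7.6 / 11.9 / 17.0 / 19.6% with 3 samples and 4.8 / 10.8 / 20.4 / 29.6 / 35.8% with 6. The test is sound at ρ = 0, so the inflation comes from the missing child term. With a subject intercept (complete data, equal SDs) the size was 4.2–5.9% throughout.

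**Unequal SDs.** H = (s²_A/n_A + s²_B/n_B) / (s²_p × (1/n_A + 1/n_B)), with s²_p = (n_A s²_A + n_B s²_B)/(n_A + n_B), where A is vaccination and B infection. Size exceeds 5% only when ρ > (1/H − 1)/(m − 1). The 60 v 20 rows are age cohort 2 alone, the most unbalanced cohort; at 20 v 20 (cohort 1), H = 1 for any SD ratio.

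| n (A v B) | SD (A v B) | H | Break-even ρ, m = 3 / 6 | Size at ρ = 0.3, m = 3 / 6 |
|---|---|---|---|---|
| 140 v 80 | 1.5 v 1 | 0.810 | 0.12 / 0.05 | 8.5% / 16.8% |
| 140 v 80 | 2 v 1 | 0.719 | 0.20 / 0.08 | 6.8% / 14.4% |
| 60 v 20 | 1.5 v 1 | 0.677 | 0.24 / 0.095 | 6.0% / 13.2% |
| 60 v 20 | 2 v 1 | 0.538 | 0.43 / 0.17 | 3.5% / 9.1% |
| 140 v 80 | 1 v 1.5 | 1.234 | none | 16% / 26% |

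**Change-from-baseline models.** Fitted per visit, they use one value per child and are not affected. If two visits sharing one baseline are pooled, then under equal correlation the two changes correlate 0.5 whatever ρ is. That gives D = 1.5 and size 11% (simulated: 10.7–11.2%).

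**The case against.** The plan calls (0.1) a linear mixed effect model, so a child effect may have been intended and lost in drafting. That is possible, but the equation and the written definitions agree in giving none, and an analyst following the text would code a random visit effect only. The text needs correcting either way.

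The covariates, age above all, may absorb much of the between-child variation. This stands as a condition: the ρ that matters is what remains after X, and the simulations included no covariates. It lowers the relevant ρ but does not replace a child term.

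Sample counts are maxima, and missed visits will not all be random, since only infected children can bypass visit 1. This also stands, and is why the 6-sample figures are upper values.

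Finally, (0.1) is an addition to time-specific tests that do not have this problem, and section 11.2 sets a modest aim: "if trends towards a relationship are discovered, subsequent studies will evaluate these in more detail". This limits the harm, but it does not make the test valid. A study meant to pick out trends for follow-up is poorly served by a test that produces them too readily.

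**Conclusion.** The concern holds: (0.1) as written is mis-specified for its group test. If the rest of the model is right and the arm variances are similar, the test is anti-conservative for any positive residual within-child correlation. At a correlation of 0.3 its true size is about 12% with 3 samples and 12–22% with 6 (complete data), depending on how much correlation carries over to the next season. The correlation, carry-over and SD ratios are assumptions, since the documents give none. If the vaccination arm is more variable and the correlation is small, the test may not be inflated; at 0.3 the only case examined without inflation was 60 v 20, SD 2 v 1, with 3 samples. The finding covers (0.1), and the change-from-baseline models only if they pool visits. It should be fixed before the final analysis; the consequence is false leads rather than a wrong confirmatory claim.

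**What to change.** In section 11.4, add a subject random intercept to (0.1), or specify a within-child residual covariance. In the same edit, write the null as β₁ₖ = 0 and define G by enrolment cohort (A = 0, B = 1) at all visits, because both arms receive IIV from season 2. State whether the change-from-baseline models are fitted per visit; if visits are pooled, give them the same child-level term.

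The cost is wording and code, with no new data, and group p-values will become less favourable. The child term removes the correlation effect only. It does not address unequal arm variances: with SD 1.5 v 1 the corrected test had simulated size 2.7–3.5% at 140 v 80 and 1.8–2.1% at 60 v 20, so it would then be conservative.

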3 OBJECTIVES AND OUTCOME MEASURES

3.1 Study Objectives

Primary Objective

To evaluate the relationship between influenza virus exposure, infection and vaccine history, and CD4 T cell reactivity in a cohort of children with well documented influenza exposures.

Exploratory Objectives

Determine the durability and breadth of the CD4 T cell and B cell/antibody responses and evaluate for relationships between response durability and factors such as age and exposure history.

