3.2.2 Exploratory Outcome Measures

- Evaluate the humoral immune response that develops in response to infection or IIV vaccination using ELISA, microneutralization, and HAI assays with stratification by age and exposure history
- Determine the frequency of influenza-specific plasmablasts and memory B cells by ELISPOT and flow cytometry, with expression of monoclonal antibodies from cloned variable genes of single cells
- Determine the influence of the CD4 T cell response on the breadth and avidity of the post-vaccination antibody response
- Compare the cellular phenotype and functional potential observed at the day 24 post vaccination visit in study year one with that present at the prevaccination study visit in year 2 and 3

[figure not shown]

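### Section 11.4 lists no analysis that directly estimates or tests the exploratory durability outcome (year 1 day 24 against the year 2 and year 3 pre-vaccination visits)

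*Combined protocol and SAP*

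**What the plan says.** Section 3.2.2 (repeated in the Protocol Summary) includes an exploratory outcome on cell phenotype and function, which compares what is "observed at the day 24 post vaccination visit in study year one with that present at the prevaccination study visit in year 2 and 3". The exploratory objective shown in Section 3.1 covers durability and breadth, and asks to "evaluate for relationships between response durability and factors such as age and exposure history".

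Section 11.4 then lists these analyses:

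- Two-sample t-tests, or Wilcoxon rank-sum tests, that "will be used to detect significant mean difference between the children of different ages and flu exposures at each time point".
- For the follow-up seasons, one-way ANOVA or Kruskal-Wallis tests "to detect significant group differences at each time point".
- "General linear models of difference or fold change in T/B cell response at following time points from baseline", adjusted for age, sex, illness and medication.
- Model (0.1), fitted to all time points. It has an overall mean, a binary arm term, confounders, a time term that "is a random effect term that quantifies the time effects", and independent measurement errors. The likelihood ratio test is of beta equal to zero.
- Variable selection by AIC, BIC, LASSO or SCAD.

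Appendix A schedules blood at Visit 3, Visit 4 and optional-season Visit 1, where it can be obtained.

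**The concern.** Durability here is a contrast between two named visits in the same child. Its dependence on age and exposure is an interaction of that contrast with arm and age cohort. No listed analysis takes day 24 as its reference, and the one model that uses all visits has no term for either quantity.

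If the plan is followed as written, the analyst has to invent the durability analysis. Section 11.3 says that assay results will be reviewed as they become available, so that choice could be made with results in view. The analyst could also read persistence from separate visit summaries or from the predicted time effects, and both discard the pairing of samples within a child.

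**Working it through.** The documents give no power, effect size or SD (Section 11.2 says that variability is unknown), so there is no plan figure to reproduce. The enrolment counts in Section 5 do agree: 20 + 60 + 30 + 30 = 140 vaccinated, 4 × 20 = 80 infected, 220 in total.

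**Step 1. What model (0.1) implies for the contrast.** Write the change for child i from Visit 3 to Visit 4. The overall mean and the arm term cancel, because neither depends on visit. What remains is

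γ(Visit 4) − γ(Visit 3) + β2 × (change in confounders) + error.

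- The γ terms carry no subject or arm index, so the modelled change is the same in both arms apart from confounders.
- The γ terms are random, so their difference is a prediction and not a parameter, and the stated test does not touch it.
- β1 is one arm difference constant over visits. With six balanced visits, an arm difference of 1 SD confined to Visit 4 would enter β1 as 1/6 = 0.17 SD, indistinguishable from a small constant difference.

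**Step 2. Simulation of model (0.1) as written.** Assumed: 30 against 20 children, six visits, SD 1, 400 runs per scenario, maximum likelihood, and a likelihood ratio test of β1 at 0.05. The true β1 is 0 throughout.

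| Scenario (mean profile over Visits 1 to 6) | Correlation 0 | Correlation 0.5 |
|---|---|---|
| Both groups hold day 24 level (0, 1, 1, 1, 1.5, 1.5) | 6% | 34% |
| Both fall 1 SD by Visit 4 (0, 1, 1, 0, 1.5, 1.5) | 5% | 29% |
| One falls 1 SD, the other holds (0, 1, 1.5, 0.5, 1.5, 1.5 against 0, 1, 1, 1, 1.5, 1.5) | 3% | 26% |

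The first two rows differ by no more than simulation noise: at correlation 0.5, 34% − 29% = 5 points, against a standard error of √(0.34 × 0.66/400 + 0.29 × 0.71/400) ≈ 3 points. The third row shows no sensitivity to different waning when the all-visit averages are equal.

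The high rates at correlation 0.5 are false positives from the missing subject effect. The variance of the arm difference is understated by 1 + 5 × 0.5 = 3.5, so the nominal 1.96 acts as 1.96/√3.5 = 1.05, a two-sided rate of about 29%.

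**Step 3. Cost of ignoring the pairing.** With correlation ρ between the two draws, the standard error of the mean change in n children is SD × √(2(1 − ρ)/n). Independent errors give SD × √(2/n), which is too large by 1/√(1 − ρ): 1.20, 1.41 and 2.24 at ρ = 0.3, 0.5 and 0.8.

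**Step 4. What a direct within-child contrast could detect.** Mean change in SD units at 80% power, two-sided 0.05, normal approximation, no missing samples, before false discovery rate adjustment: (1.96 + 0.84) × √(2(1 − ρ)/n).

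| n | ρ = 0.3 | ρ = 0.5 | ρ = 0.8 |
|---|---|---|---|
| 20 (one infection cohort, or 1A) | 0.74 | 0.63 | 0.40 |
| 30 (3A or 4A) | 0.61 | 0.51 | 0.32 |
| 60 (2A) | 0.43 | 0.36 | 0.23 |
| 140 (all vaccinated) | 0.28 | 0.24 | 0.15 |

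For n = 20 and ρ = 0.5, 2.80 × √(1/20) = 0.63. Treated as unpaired, the same data give 2.80 × √(2/20) = 0.89. In year 3, n falls to about two-thirds (Section 5), or 220 × 2/3 ≈ 147 children overall.

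**The case against.** The strongest reply is that the general linear models already give within-child changes related to exposure and adjusted for age. The Visit 4 change minus the Visit 3 change, both from Visit 1, is exactly the wanted quantity. Ignoring a positive correlation makes the comparison inefficient, but it does not bias the mean change. The outcome is also exploratory, and Section 11.2 leaves trends to later studies.

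Most of this stands. A reader might infer that no valid estimate of durability is possible under the plan, and the documents do not support that. The differencing route has three gaps, however:

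- Neither the subtraction nor its standard error is listed.
- The plan does not say whether baseline in year 2 means year 1 Visit 1 or that season's own pre-vaccination draw. Under the second reading these models cannot give the contrast.
- Section 7.2 lets some infected children bypass Visit 1. They would have no change from baseline, although they may have both draws that the contrast needs.

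A reader might also take the shrinkage of the random time effects as the main fault. It is not. If the visit variance is one tenth of the residual variance (an assumption), the predicted contrast keeps 0.1/(0.1 + 1/220) = 96% of its size with all 220 children, a loss of about 4%. It falls to 0.1/(0.1 + 1/40) = 80% only if one age cohort of 40 is fitted alone.

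**Conclusion.** The gap is real and should be closed. Section 11.4 has no analysis that directly estimates or tests the change from year 1 day 24 to the next pre-vaccination visits, and none that tests whether this change differs by arm or age. Model (0.1) as written cannot do so, and the general linear models reach it only through an unlisted step and one reading of baseline.

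The consequence is limited. The outcome and objective are labelled exploratory, the samples are scheduled, and the primary CD4 outcome does not depend on this contrast. The claim about what the plan lists rests on its text alone. The rejection rates, standard error ratios and detectable changes rest on assumed correlations, an SD of 1 and assumed mean profiles, because the documents give none of these.

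**What to change.** In model (0.1), make visit a fixed categorical factor, add a subject random effect (or an unstructured within-child covariance), and add arm-by-visit and age-cohort-by-visit terms. Making visit fixed is not enough by itself, because independent errors would still ignore the pairing.

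Then prespecify in Section 11.4, labelled exploratory:

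- **Contrasts.** Visit 4 minus Visit 3, and optional-season Visit 1 minus Visit 3, within child, on a log scale where suitable and with a stated rule for undetectable values. A simpler route to the same quantity is a linear model of each child's change on arm, age cohort and centred days between draws.
- **Reporting.** Give the adjusted mean change by arm and cohort as the persistence estimate, and the arm and cohort terms as the test of the factors in the objective. An uncentred intercept will not serve: it is the change in the reference arm and cohort at zero days between draws, far outside the data.
- **Infection cohorts.** State that their Visit 3 is day 24 after illness presentation (Section 7.3), whereas the outcome is worded as post vaccination.
- **Re-exposure.** Run a sensitivity analysis that excludes or flags children with documented or serologically suspected influenza between the two draws. Section 2.2 already expects the pre-vaccination draw to help detect undocumented infection, so the raw change mixes waning with boosting.
- **Definitions.** Define baseline for seasons 2 and 3, and say whether these contrasts join the Benjamini-Hochberg family.

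The cost is SAP wording, a little more analysis on samples already scheduled, and more parameters. Over six visits and four age cohorts these are 5 visit, 5 arm-by-visit and 3 × 5 = 15 cohort-by-visit terms, in about 220 children.

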8.2.2 Laboratory Evaluations

Detection and quantification of influenza virus: Influenza will be detected from potentially infected subjects by (1) rapid antigen testing using a commercial assay (BinaxNOW, Alere, Waltham, MA or QuickVue Influenza A+B test, Quidel, San Diego, CA) and (2) real time RT-PCR using primers obtained from BEI Resources (Manassas, VA) or using the ABI 7500 real-time PCR platform. Two UV-sterilized soft nylon flocked swabs will be used to collect nasal swab samples from subjects potentially infected with influenza. One swab will be used for rapid antigen detection on site, while the other will be placed into 1 mL of viral culture transport media for use in real time RT-PCR to detect and quantify influenza viral load. This sample will be stored and may be used to sequence the infecting influenza virus at a later time point.

Multiparameter flow cytometry: PBMCs will be thawed, rested overnight, and, when appropriate, stimulated with influenza-specific peptide pools as experimental antigens, Staphylococcal enterotoxin B (a superantigen) as a positive control, or a pool of irrelevant peptides from the Sin Nombre virus glycoprotein precursor protein or media alone as a negative control for 10-20 hours, with Brefeldin A and monensin added to inhibit cytokine secretion for the final 8 hours of incubation. Cells will then be stained with a viability marker and a panel of antibodies against surface markers. When appropriate, they will then be fixed, permeabilized, and stained intracellularly using antibodies against cytokines as well as other markers. All events will be collected on a flow cytometer within the University of Rochester Medical Center Flow Core. We have the flexibility to adjust and modify these panels as necessary to optimize

our staining results.

Multiplex cytokine assay: Multiplex cytokine assays will be used to determine the antigen-specific cytokine production potential of the total CD4 T cell population. Cells will be thawed, rested overnight, and depleted of CD8 and NK cells. They then will be stimulated with HA and NP peptide pools or irrelevant peptides as a negative control. Following around 48 hours of coculture, supernatants will be assayed for levels of 30 common cytokines and chemokines with a human cytokine/chemokine magnetic bead panel (Bio-Rad Laboratories, Hercules, CA) and analyzed on a Bio-Plex200 system.

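### Section 11.4 treats being kept by AIC or BIC as significance, but sets no error level for the selection step and does not protect exposure group or the listed confounders from being dropped

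*Combined protocol and SAP*

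**What the plan says.** The selection step is described in the closing paragraph of section 11.4, after the mixed model. It opens: "In case of high-dimensional data in different scales, standardization will be applied before model fitting and variable selection". It continues: "Variable selection approaches using AIC or BIC criteria will be used to select the significant predictors". It then adds an option: "Penalized-based variable selection procedures such as LASSO [39] or SCAD [40,41] may be used to overcome the drawbacks of ad-hoc methods". The paragraph gives no candidate list, no choice between AIC and BIC, no tuning rule for the penalized methods, no error level, and no validation or resampling.

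Earlier in the same section, Benjamini-Hochberg adjustment is specified "to control the false discovery rate (FDR) at the level of 0.05". The reason given is "Because multiple response variables are used in this analysis", and the sentence follows the t-test, rank-sum, ANOVA and Kruskal-Wallis comparisons between groups.

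Between these two places, section 11.4 describes general linear models and a mixed model for the effect of exposure. They adjust for age, sex, asthma or allergies, other illnesses and medications.

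**The concern.** A predictor that survives AIC or BIC has improved a penalized fit. It has not passed a test at a stated level. If the plan is followed as written, noise terms can be reported as significant at a rate that depends on a criterion not yet chosen and, for BIC, on the sample size. The word would also carry two meanings within section 11.4: adjusted at a false discovery rate of 0.05 for group comparisons, and retained by a criterion for predictors. A reader of the results could not tell them apart.

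Two things are at stake. Section 11.2 says that trends found here will be examined in later studies, so a list of significant predictors is an output that others will act on. And if selection is free to remove a real confounder, the estimated effect of exposure, which is the subject of the primary objective, can be biased.

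**Working it through.** The documents give no error rate for the selection step, so there is no stated figure to reproduce. The check derives what the rule implies.

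**Inputs from the documents**
- Criterion: AIC or BIC (section 11.4). The penalty per added parameter is 2 for AIC and ln(n) for BIC.
- n for the whole study: 220. Section 5: "It is anticipated that this study will enroll a total of approximately 220 subjects".
- n for one age cohort: 40 to 80, from 20 to 60 vaccinated plus 20 infected. Section 11.4: "n=20 children infected with influenza acutely will be recruited for each age cohort".

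**Assumption**
- Number of candidates: not given. For illustration 30 is used, the size of one assay panel in section 8.2.2: "supernatants will be assayed for levels of 30 common cytokines and chemokines". The plan does not name these analytes as candidate predictors. Independence between candidates is also assumed.

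**Step 1. One added noise term, large sample.** The term is kept if its likelihood-ratio statistic exceeds the penalty, and under the null that statistic is chi-square with 1 df.
- AIC: P(chi-square > 2) = 0.157 at any n.
- BIC, n=40: ln 40 = 3.69, P = 0.055.
- BIC, n=80: ln 80 = 4.38, P = 0.036.
- BIC, n=220: ln 220 = 5.39, P = 0.020.
- BIC matches a 5% test when ln(n) = 3.84, that is at n of about 47.

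**Step 2. Small-sample form.** For Gaussian data and one term added to an intercept, the term is kept if F on 1 and n−2 df exceeds (n−2)(exp(penalty/n) − 1). For AIC at n=40 the cut-off is 38 × (exp(0.05) − 1) = 1.95, giving P = 0.171. At n=80 and n=220 AIC gives 0.164 and 0.160. BIC gives 0.063, 0.039 and 0.021 at n=40, 80 and 220.

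**Step 3. Stepwise search.** Forward selection was simulated on all-noise data with 30 independent candidates, 3,000 runs per setting. Entries are retention rates per candidate.

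| n | AIC | BIC |
|---|---|---|
| 40 | 0.29 | 0.087 |
| 80 | 0.20 | 0.045 |
| 220 | 0.17 | 0.022 |

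The single-term rates of step 1 are therefore low for a search in one age cohort, and close to right at n=220.

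**Step 4. Illustrative counts, 30 noise candidates, single-term rates.**
- AIC: 30 × 0.157 = 4.7 kept on average; P(at least one) = 1 − (1 − 0.157)^30 = 0.99.
- BIC, n=40: 30 × 0.055 = 1.6; P(at least one) = 0.82.
- BIC, n=220: 30 × 0.020 = 0.6; P(at least one) = 0.46.

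**Step 5. Illustrative false share of the selected set.** Add s true predictors, all found, with s = 5 to 10. The approximate false share is 30p/(30p + s).
- AIC: 4.72/14.72 = 32% to 4.72/9.72 = 49%.
- BIC, n=40: 1.64/11.64 = 14% to 1.64/6.64 = 25%.
- BIC, n=220: 0.61/10.61 = 6% to 0.61/5.61 = 11%.
- Plain p<0.05, for comparison: 1.5/11.5 = 13% to 1.5/6.5 = 23%.

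**The case against.** The strongest reply is that no stated level is breached. A reader might infer that predictors chosen this way fail the plan's own 5% level. The text does not support that: the 5% false discovery rate is attached to comparisons across response variables, and nothing extends it to selection. Nor can 0.16 be set directly against 5%. The first is a retention probability per noise term; the second is an expected false share of a list, which depends on numbers of true and noise predictors that the plan does not give. Step 5 shows that even an unadjusted 5% test per term would not deliver a 5% false share. This part of the reply stands.

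It is also fair to say that:
- the plan allows BIC, which at n=220 is stricter than a 5% test per term, so a long list of false leads is not inevitable;
- the assay readouts may enter mainly as responses, so 30 is not a count of candidates;
- the study is presented as a search for trends, and the section itself acknowledges weaknesses of ad-hoc selection and offers LASSO or SCAD.

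These limit the size of the problem without removing it. The penalized methods are optional and come with no tuning rule or error level, so the acknowledged weakness has no committed remedy.

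On confounders, the models specified just before do include exposure group and clinical covariates. It would go too far to say that the plan intends to drop them. What stands is that the selection paragraph names no protected terms.

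**Conclusion.** The point holds as a gap in the selection rule. Section 11.4 equates retention by AIC or BIC with significance, leaves the criterion open, sets no error level for this step, and does not protect exposure group or the listed confounders. For a single added noise term the retention rate is about 0.16 with AIC and 0.055 (n=40) to 0.020 (n=220) with BIC, and it is higher in stepwise search in small samples. These rates need only the null distribution of the likelihood-ratio statistic and the planned sample sizes. The counts and false shares rest on further assumptions: 30 candidates, independence, and 5 to 10 true predictors all found. They show scale and do not predict this study's results.

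The matter is minor in an exploratory study, but it decides what the study may call significant.

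**What to change.** Change the selection paragraph of section 11.4 as follows.

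1. Keep exposure group and the confounders already listed in that section in every model, and let selection act only on additional predictors.
2. Reserve 'significant' for Benjamini-Hochberg-adjusted tests computed over all candidate predictors. P-values taken from the selected model must not be used for this, because they ignore the search that produced the model.
3. Report AIC, BIC, LASSO or SCAD selections as exploratory candidates, with cross-validated error or the frequency of selection under resampling. The selection should be repeated inside each fold or resample.
4. State the candidate set, which criterion applies and, if a penalized method is used, its tuning rule.

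The cost is SAP wording and a little more computing, with no new data or visits. The downside is that fewer predictors can be called significant.
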